Study design		Using a traditional "3+3" dose-escalation design, subjects will be sequentially assigned to one of three dose groups (2.8×10^{10} units, 1.4×10^{11} units, and 7.0×10^{11} units per dose, once daily, with continuous intranasal instillation for 4 days). Each dose group will include 3 subjects, who will be enrolled one by one. The exploration of the next dose can only proceed if no dose-limiting toxicity (DLT) is observed in the 3 subjects. If 1 out of the 3 subjects experiences DLT, an additional 3 subjects will be enrolled in the same dose group; the exploration of the next dose can only move forward if no DLT is observed in these newly added 3 subjects. A minimum of 6 and a maximum of 18 subjects will be recruited during the dose exploration phase. Patients will receive other standard medical treatments in accordance with the recommendations in the 2022 Chinese Guidelines for Secondary Prevention of Ischemic Stroke and Transient Ischemic Attack , including antiplatelet drugs or anticoagulants, antihypertensive drugs, lipid-lowering drugs, and glucose-lowering drugs.
Outcome Measures	Primary Outcome Measure	Dose-Limiting Toxicity (DLT) Related to hUC-MSC-sEV-001 Includes: (1) Grade 3-4 severe adverse events occurring on day 14 (+-2), graded according to Common Terminology Criteria for Adverse Events (CTCAE) V5.0; (2) NIHSS score increase of ≥ 4 from baseline on day 14 (+-2); NIHSS score assessed by a professional rehabilitation physician;(3) Symptomatic intracranial hemorrhage occurring on day 14 (+-2); detected via CT scan and patient symptom presentation.
	Secondary Outcome Measures:	Serious adverse events related to the investigational drug within 90 (+-7) days. Distribution of Modified Rankin Scale (mRS) Scores within 90 (+-7) days. Barthel Index within 90 (± 7) days. Five-level, five-dimensional EuroQol (EQ-5D-5L) . Proportion of Modified Rankin Scale (mRS) Scores of 0-2 within 90 (+-7) days. All-cause mortality at 90 (+-7) days. Changes in infarct volume at 14 (+-2) days compared to baseline. Change from Baseline in National Institutes of Health Stroke Scale (NIHSS) Score.
Follow-up duration		Baseline (0~1 day), 7 (± 1) days, 14 (± 2) days, 90 (± 7) days
Sample size		6-18 subjects need to be included.

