Furthermore, this research will greatly promote the translational application of MSC-sEVs in the treatment of other diseases, provide a scientific basis for the government to improve the treatment system for stem cells and their derivatives, enhance the level of patient care, reduce mortality and disability rates, and benefit a large number of patients—thereby generating substantial economic and social benefits. It will also accelerate the rapid development of MSC-sEV applications, align with the national strategy of promoting innovation-driven development, and play a positive role in safeguarding the growth of social and economic benefits.

Main Research Content

Based on adherence to the Good Clinical Practice (GCP) principles for national clinical trial research and the standardized procedures of Contract Research Organizations (CROs), this study aims to evaluate the safety and preliminary efficacy of hUC-MSC-sEV-001 in the treatment of ischemic stroke by enrolling a small sample population. Additionally, the study will explore and determine an appropriate dose to lay the foundation for subsequent research.

Research Methods

Clinical-grade hUC-MSC-sEV-001 produced under Good Manufacturing Practice (GMP) conditions will be obtained, and standardized procedures compliant with clinical research requirements will be established, covering aspects such as production, testing and identification, storage and resuscitation, transportation and packaging, and quality control.

Clinical research protocols, investigator's brochures, case report forms (CRFs), informed consent forms (ICFs), and recruitment advertisements will be developed, followed by submission for approval to the Ethics Committee (EC).

In accordance with the research protocol, 6–18 volunteers with ischemic stroke will be recruited to preliminarily explore the safety of hUC-MSC-sEV-001 in the treatment of cerebral ischemia. The optimal therapeutic and safe dose derived from animal experiments will be converted, and the corresponding treatment route and frequency will be determined. Safety assessments—including changes in vital signs and adverse reactions after treatment—will be conducted at baseline (Day 0–1), Day 7 (± 1), Day 14 (± 2), and Day 90 (± 7). Additionally, efficacy will be evaluated from the perspectives of laboratory indicators, imaging findings, neurological function assessment indicators, and follow-up data.

1. Study Design

(1) Overall Study Design

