Single-center, prospective, dose-escalation clinical trial.

(2) Trial Administration Strategy

A traditional "3+3" dose-escalation design will be adopted. Subjects will be sequentially assigned to one of three dose groups (2×10^{10} units, 1×10^{11} units, 5×10^{11} units per administration, once daily for 4 consecutive days via intranasal instillation). Each dose group initially enrolls 3 subjects, with sequential enrollment (i.e., the next subject is enrolled only after the previous subject completes the 14-day DLT observation period).

- If no DLT is observed in 3 subjects of a dose group, the study proceeds to the next higher dose level.

- If 1 out of 3 subjects experiences DLT, an additional 3 subjects are enrolled in the same dose group. If no DLT is observed in the additional 3 subjects, the study proceeds to the next higher dose level; if ≥ 1 additional subject experiences DLT, the current dose level is defined as the maximum tolerated dose (MTD), and dose escalation is terminated.
- A total of 6 to 18 subjects will be recruited during the dose-escalation phase.

(3) Study Suspension or Early Termination

The study will be suspended or terminated early if any of the following occurs:

- Violation of the *Good Clinical Practice (GCP)* or the *Administrative Measures for Stem Cell Clinical Research (Trial)*;
- Emergence of new safety or efficacy data on MSC-sEVs indicating that the trial poses a serious risk to patient safety or is clearly ineffective;
- Failure to enroll subjects as scheduled for 3 consecutive months;
- Major protocol deviations that affect the validity of study data;
- Request for termination by the sponsor or regulatory authorities.

2. Subject Selection Criteria

(1) Inclusion Criteria

- Confirmed diagnosis of acute ischemic stroke (in accordance with the *Chinese Guidelines for the Diagnosis and Treatment of Acute Ischemic Stroke (2023)*);
- Aged 18-70 years, regardless of gender;
- Anterior circulation occlusion (internal carotid artery, middle cerebral artery M1/M2 segment) confirmed by CTA or MRA;
- mRS score of 0-1 before the current stroke episode (indicating no or minimal disability prior to the index event);
- ASPECTS ≥ 6 on non-contrast computed tomography (NCCT) or diffusion-weighted imaging (DWI) after stroke onset (indicating a small to moderate infarct volume);
- NIHSS score ≥ 6 at screening (indicating moderate to severe neurological deficit);

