- Confirmation of the MTD or identification of an unsafe dose level;
- Major flaws in the study design that affect data validity;
- Regulatory requirements (e.g., request by the National Medical Products Administration [NMPA]).

. Subject Withdrawal

Subjects may withdraw from the study at any time for the following reasons:

(1) Investigator-determined withdrawal:

① The subject develops a medical condition that makes continued participation unsafe (e.g., severe allergic reaction, intracranial hemorrhage);② The subject uses medications that interact with the study drug (e.g., immunosuppressants) or affect efficacy assessment (e.g., edaravone);③ The subject experiences a SAE that requires termination of study participation;④ The subject has poor compliance that compromises the reliability of safety or efficacy data.

(2) Subject-initiated withdrawal:

① The subject voluntarily requests to withdraw (no reason required);② The subject is lost to follow-up (no contact for ≥ 2 weeks).

For withdrawn subjects, the investigator shall conduct a final safety assessment (if possible) and document the reason for withdrawal in the CRF. Subjects who withdraw due to AEs/SAEs shall receive appropriate medical treatment, and follow-up shall continue until the AE/SAE resolves or stabilizes.

(7) Criteria for Terminating the Study

The study will be terminated immediately if any of the following occurs:

≥ 2 subjects experience DLT at the same dose level (indicating that the dose exceeds the MTD);

- Production of hUC-MSC-sEV-001 fails to meet quality standards for 3 consecutive batches, resulting in inability to administer scheduled doses;

- The study drug is found to have no clinical benefit (e.g., no improvement in neurological function in all enrolled subjects) or is associated with unexpected severe toxicity;
- A major protocol deviation is identified (e.g., incorrect randomization, unapproved dose modification) that invalidates the study results;
- The sponsor terminates the study due to funding, strategic adjustments, or other reasons;
- The Ethics Committee or NMPA issues an order to terminate the study.

3. Intervention Measures

(1) Trial Drug

- **Generic Name:** Human Umbilical Cord Mesenchymal Stromal Cell-Derived Small Extracellular Vesicle (hUC-MSC-sEV-001) Nasal Drops
- **Source:** Isolated and purified from the supernatant of hUC-MSCs cultured under GMP conditions

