 - Grade ≥ 3 laboratory abnormalities are summarized as frequency (percentage) by dose group.

(4) Sample Size Justification

This is a phase I dose-escalation study designed to explore the safety and MTD of hUC-MSC-sEV-001. Using the "3+3" design, a sample size of 6-18 subjects is sufficient to identify the MTD with a 90% probability of avoiding overdosing and a 80% probability of identifying the MTD if it exists.

(5) Statistical Software

All statistical analyses are performed using SAS 9.4 software (SAS Institute Inc., Cary, NC, USA). Two-sided tests are used, and a P-value < 0.05 is considered statistically significant.

(6) Interim Analysis

No interim analysis is planned for this study due to the small sample size. The study will be terminated early only if safety concerns arise (e.g., ≥ 2 subjects experience DLT at the same dose level).

12. Quality Control and Assurance

(1) Protocol Compliance

- **Training:** All study personnel (investigator, CRC, monitor, pharmacist) receive training on the study

protocol, GCP, and stem cell clinical research regulations before study initiation. Training records are retained in the study file.

- **Standard Operating Procedures (SOPs):** SOPs are developed for key processes, including subject screening, study drug administration, adverse event reporting, and data management. Study personnel strictly follow the SOPs to ensure consistency.
- **Protocol Deviation Monitoring:** The monitor records all protocol deviations (e.g., missed visits, incorrect dose administration) in the "Protocol Deviation Log". Major deviations are reported to the Ethics Committee and sponsor.

(2) Study Drug Quality Control

- **Manufacturing Quality:** The study drug is produced under GMP conditions, and each batch is tested for purity, potency, sterility, and endotoxin levels. A certificate of analysis (CoA) is provided for each batch.
- **Storage and Transportation:** Temperature monitoring during transportation and storage ensures that the study drug remains within the specified temperature range (-80°C ± 10°C). Temperature records are reviewed and archived.
- **Inventory Management:** The study drug inventory is checked monthly to ensure that the quantity administered matches the quantity received, and to prevent expiration or loss.

(3) Laboratory Quality Control

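### The 90% and 80% probabilities that justify the sample size are not general properties of this 3+3, and 6 is not the minimum number of subjects under the protocol's own stopping rules

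*Protocol*

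**What the plan says.** Section 11(4) of the protocol rests the sample size of 6–18 on the statement that the 3+3 has "a 90% probability of avoiding overdosing and a 80% probability of identifying the MTD if it exists". No other justification is given.

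The range appears in several places. The synopsis says "A minimum of 6 and a maximum of 18 subjects will be recruited during the dose exploration phase". Section 1(2) says "A total of 6 to 18 subjects will be recruited during the dose-escalation phase". Under Research Methods, 6–18 is the number of "volunteers with ischemic stroke will be recruited to preliminarily explore the safety of hUC-MSC-sEV-001".

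The rules that determine these quantities are:

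- **Section 1(2):** three dose levels. No DLT in 3 subjects leads to escalation. One DLT in 3 leads to 3 more subjects, with escalation only if none of them has a DLT. Enrolment is one by one: "the next subject is enrolled only after the previous subject completes the 14-day DLT observation period".
- **Section 1(2), MTD:** after one DLT in the first 3, if at least one "additional subject experiences DLT, the current dose level is defined as the maximum tolerated dose (MTD), and dose escalation is terminated". The section does not say what follows 2 or 3 DLTs in the first 3 subjects.
- **Section 2(7):** the whole study stops at once when at least two "subjects experience DLT at the same dose level (indicating that the dose exceeds the MTD)".
- **Section 11(6):** "The study will be terminated early only if safety concerns arise", with two DLTs at one level as the example.

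**The concern.** In a 3+3, the chance of selecting the right dose, or one that is too high, is set by the unknown dose-toxicity curve. A single pair of percentages has meaning only with a stated curve, target rate and definition of overdosing. Section 11(4) gives the pair without conditions, as if it followed from the design and the number of subjects.

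One of the two figures is a safety assurance. The Ethics Committee and sponsor would read it as a known property of the trial. The true values also depend on which MTD rule applies, and on this Sections 1(2) and 2(7) give opposite labels to the same data: one DLT in 3 followed by another makes the current dose the MTD in the first, and a dose above the MTD in the second.

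The lower limit of 6 is a separate point. One-by-one entry combined with stopping at the second DLT allows smaller totals.

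**Working it through.** **Inputs from the protocol.** Three levels; 0/3 escalates; 1/3 adds three; 1/3 then 0/3 escalates; the study stops at two DLTs at a level; one-by-one entry.

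**Assumptions, not in the protocol.** MTD = highest dose with a true DLT rate of at most 33%. Overdosing = selecting a dose above the MTD. Under the Section 2(7) reading the selected dose is the level below the one that fails.

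**The plan's own figures.** The 90% and 80% cannot be reproduced, because their inputs are not given. The maximum can: 3 levels × 6 subjects = 18.

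**Step 1: passing a level.** With DLT rate p and q = 1 − p,

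P(pass) = q³ + 3pq² · q³.

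This gives 0.973 at p = 5%, 0.906 at 10%, 0.814 at 15%, 0.709 at 20%, 0.600 at 25%, 0.309 at 40%, 0.234 at 45%, 0.172 at 50% and 0.082 at 60%.

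**Step 2: selection under the Section 2(7) reading.** P(correct) is the product of the pass probabilities up to the MTD, times the fail probability at the next level. For 5/15/45% the MTD is level 2:

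- P(correct) = 0.973 × 0.814 × (1 − 0.234) = 0.607
- P(overdose selected) = 0.973 × 0.814 × 0.234 = 0.186

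| True DLT rates | P(correct) | P(overdose selected) |
|---|---|---|
| 5/15/45% | 61% | 19% |
| 5/25/50% | 48% | 10% |
| 10/25/40% | 38% | 17% |
| 20/40/60% | 49% | 22% |

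All four fall well short of 80% correct. Only 5/25/50% reaches 90% avoidance, and only after rounding.

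Some curves meet both figures: 14/70/82% gives 81% correct and 3% overdose, and 5/10/60% gives 81% and 7%. With 2/5/8% the top dose is selected in 91% of runs and overdose selection is impossible.

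**Step 3: a wider range of curves.** Take rates from 2% to 90% in steps of 4 points, increasing across levels, with the lowest dose at or below 33% and the top dose above it. This gives 1,260 curves. The counts are unweighted and are not probabilities.

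| Reading | 80% met | 90% met | Both met |
|---|---|---|---|
| Section 2(7) | 186 (15%) | 644 (51%) | 157 (12%) |
| Section 1(2) | 89 (7%) | 178 (14%) | 54 (4%) |

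For the Section 1(2) row, 1/3 followed by at least one more DLT makes the current dose the MTD. Two or more DLTs in the first 3 are assumed to select the level below, since that section is silent.

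Sensitivity under the Section 2(7) reading (80% met / 90% met / both):

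- target 25%: 17% / 36% / 15%
- target 20%: 20% / 30% / 17%
- rates capped at 70% (640 curves): 7% / 37% / 5%
- adding curves with a tolerable top dose (1,316 curves): 14% / 53% / 12%

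**Step 4: a stricter meaning of overdosing.** Suppose overdosing means that any subject is treated above the MTD, and the MTD lies below the top level.

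- *Section 2(7) reading.* The MTD is identified only by treating, and failing, the level above. So P(identify) + P(avoid) ≤ 100%, while the claims add to 80% + 90% = 170%.
- *Section 1(2) reading.* The two claims together need P(identify and avoid) ≥ 0.80 + 0.90 − 1 = 0.70. The only such path is 1/3 then at least one more DLT at the MTD level. Its probability is at most 3pq²(1 − q³), which for p ≤ 1/3 peaks at 3 × 0.333 × 0.444 × (1 − 0.296) = 0.313.

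The two claims therefore cannot both hold under this definition.

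**Step 5: the minimum size.** Two DLTs in the first two subjects end the study at N = 2. Level 1 can also end it at 3, 4 or 5. No DLT in 3 at level 1, then DLTs in the first two subjects at level 2, ends it at 5. Clearing all levels with no DLT takes 3 × 3 = 9.

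With p₁ and p₂ the DLT rates at levels 1 and 2,

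P(N < 6) = p₁² + 2p₁²q₁ + 3p₁²q₁² + 3p₁²q₁³ + q₁³p₂².

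For 20/40/60%: 0.040 + 0.064 + 0.0768 + 0.0614 + 0.0819 = 0.324.

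| True DLT rates | P(N < 6) | Expected N |
|---|---|---|
| 5/15/45% | 4% | 9.9 |
| 5/25/50% | 7% | 9.2 |
| 10/25/40% | 12% | 9.2 |
| 20/40/60% | 32% | 7.2 |

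At 2/5/8%, P(N < 6) is 0.6%.

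**The case against.** Four points can be made for the plan.

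- **The figures are attainable, and their inputs may sit in an analysis plan not shown.** Missing inputs alone would not be a finding. What stands is that the protocol itself states the two numbers without conditions. A separate document could supply the conditions, but it could not make the figures true of the design in general.
- **The grid proves little.** About half of its curves have a top-dose rate above 70%, and low-toxicity curves are barely sampled. Curves such as 1/2/5%, 2/5/8%, 3/6/10% and 5/8/10% give 97%, 91%, 86% and 83% correct selection with no possible overdose selection. This is fair: the percentages are not chances that the claim is true, and the named curves carry the argument. Capping the rates at 70% makes the claims fail more often, so the direction does not come from the extreme curves.
- **Six fits Section 1(2) read alone.** With full cohorts, the only path there that declares an MTD uses at least 6 subjects, and clearing all levels takes 9 to 18. This is correct, but Sections 2(7) and 11(6) also apply and allow the study to stop sooner. The minimum is therefore a conflict between sections.
- **No escalation decision depends on the sentence.** This is true. It limits the consequence but does not make the statement correct.

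**Conclusion.** The concern holds. The 90% and 80% are unsupported as stated and are not generally true of this design. The 80% figure fails for most curves examined. The 90% figure holds for about half of them under the Section 2(7) reading and for 14% under the Section 1(2) reading. These results rest on the assumed 33% target, on overdosing meaning selection above the MTD, and on the chosen curves; targets of 20% and 25% lead to the same conclusion. If overdosing means treating anyone above the MTD, the two figures are incompatible whenever the MTD lies below the top level.

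The minimum of 6 is wrong under one-by-one entry with termination at two DLTs, and this needs no assumed DLT rates. The smallest possible total is 2. The ceiling of 18 is right, and the escalation rules are unaffected. The correction should be made because this sentence is the only justification given for the sample size.

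**What to change.** In Section 11(4), do one of the following:

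- delete the sentence with the two probabilities and say that the size is the conventional 3+3, with no probability claimed; or
- first reconcile Sections 1(2) and 2(7) on what two or more DLTs at a level mean for the MTD, then give exact operating characteristics: the probability of selecting each level, the probability of overdosing and the expected number of subjects. State the DLT curves, target rate and definition of overdosing used.

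Restate the size in the synopsis, Research Methods, Section 1(2) and Section 11(4) to match the reconciled rules. As the rules now stand, it is up to 18 subjects, 9 if all levels clear without a DLT, and possibly fewer than 6 if the study stops at level 1 or early in level 2.

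The cost is wording and a short calculation, with no extra patients. The stated figures will probably look less favourable.

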- **Source Documents:** Medical records, laboratory reports, imaging films, and informed consent forms are stored in the hospital's medical record department or study office for 30 years after study completion.
- **Electronic Data:** The EDC database and backup files are stored on a secure server with restricted access. The data are retained for 30 years after study completion.
- **Statistical Analysis Data:** The locked database and statistical analysis code are stored in a secure location and retained for 30 years after study completion.

11. Statistical Analysis

(1) Statistical Analysis Sets

- **Full Analysis Set (FAS):** Includes all randomized subjects who receive at least one dose of the study drug. Missing efficacy data are imputed using the last observation carried forward (LOCF) method.
- **Per Protocol Set (PPS):** Includes subjects in the FAS who comply with the study protocol (e.g., complete all visits, receive all 4 doses of study drug, no major protocol violations). This set is used for sensitivity analysis of efficacy outcomes.
- **Safety Analysis Set (SAS):** Includes all subjects who receive at least one dose of the study drug. This set is used for safety analyses (adverse events, laboratory abnormalities).

(2) Descriptive Statistics

- **Continuous Variables:** Presented as mean \pm standard deviation (SD) for normally distributed data, or

median (P25, P75) for non-normally distributed data. Examples include age, NIHSS score, and infarct volume.

- **Categorical Variables:** Presented as frequency (percentage). Examples include gender, hypertension status, and mRS score categories (0-2 vs. 3-6).

(3) Inferential Statistics

- **Primary Efficacy Endpoint:** The proportion of subjects with mRS score 0-2 at Day 90 is compared between dose groups using the chi-square test or Fisher's exact test. A generalized linear model is used to adjust for potential confounders (e.g., age, baseline NIHSS score).
- **Secondary Efficacy Endpoints:**
 - Mean changes in NIHSS, MBI, and EQ-5D-5L scores from baseline are compared using repeated measures analysis of variance (ANOVA) or Kruskal-Wallis rank sum test.
 - The proportion of subjects with NIHSS score reduction ≥ 4 points at Day 14 is compared using the chi-square test.
- **Safety Endpoints:**
 - The incidence of AEs and SAEs is compared between dose groups using the chi-square test or Fisher's exact test.

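### Section 11 calls any P<0.05 among seven between-dose tests in cohorts of 3 to 6 significant, without saying that these P-values are nominal (minor)

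*Protocol*

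**What the plan says.** The tests stand in Protocol section 11(3), under the heading Inferential Statistics.

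- Primary efficacy: "The proportion of subjects with mRS score 0-2 at Day 90 is compared between dose groups using the chi-square test or Fisher's exact test". An adjusted analysis is added: "A generalized linear model is used to adjust for potential confounders (e.g., age, baseline NIHSS score").
- Secondary efficacy: "Mean changes in NIHSS, MBI, and EQ-5D-5L scores from baseline are compared using repeated measures analysis of variance (ANOVA) or Kruskal-Wallis rank sum test". This is three outcomes.
- Secondary efficacy, responders: "The proportion of subjects with NIHSS score reduction ≥ 4 points at Day 14 is compared using the chi-square test". No exact alternative is offered here.
- Safety: "The incidence of AEs and SAEs is compared between dose groups using the chi-square test or Fisher's exact test". This is two outcomes.
- Laboratory abnormalities of Grade 3 or higher are not tested; these "abnormalities are summarized as frequency (percentage) by dose group".

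That makes seven tested outcomes, not counting the adjusted mRS model. Section 11(5) applies a single rule to all of them: "Two-sided tests are used, and a P-value < 0.05 is considered statistically significant".

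On size, section 1(2) says "A total of 6 to 18 subjects will be recruited during the dose-escalation phase", with three subjects per dose at first and three more if one DLT occurs. Subjects go to the doses in sequence. The full analysis set definition in 11(1) speaks of randomised subjects, but section 1(2) describes no randomisation.

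**The concern.** A significance rule applied to a list of outcomes tells the reader of the final report how to label each result. Here the label is available to any of seven tests, with no testing order and nothing to mark the P-values as nominal. Section 5(4) lists as exploratory endpoints only infarct volume, perfusion and correlations, so the seven tested outcomes fall outside that heading. Section 13(2) likewise has the final report present efficacy results separately from exploratory ones.

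At stake is interpretation. The report goes to the Ethics Committee and the NMPA, and the results go to a journal (sections 13(2) and 13(3)). An isolated P<0.05 between cohorts of three would be weak evidence of a dose effect. Chance aside, cohorts recruited one after another can differ in case mix and in care over time.

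**Working it through.** **The plan's own figure.** The protocol gives 0.05 per test and no familywise rate, so there is no stated figure to reproduce.

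**Inputs from the protocol.** Seven tests (section 11(3)); threshold 0.05 two-sided (11(5)); three doses with 3 to 6 subjects each (1(2)).

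**Inputs assumed, because the protocol gives none.** mRS 0-2 in 40%, NIHSS responders 50%, any AE 70%, SAE 15%; correlation between outcomes 0, 0.5 or 0.8; no dose effect.

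**Reference value.** Seven independent tests, each of exact size 5%: 1 − 0.95^7 = 30.2%.

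**Null simulation of the seven tests as listed.** There were 4,000 trials per setting. The responder test was chi-square throughout. mRS, AE and SAE used Fisher or chi-square, as the protocol allows either. One-way ANOVA on the change score stood in for repeated measures ANOVA; Kruskal-Wallis used its chi-square reference. Entries are the chance (%) of at least one P<0.05 at correlation 0 / 0.5 / 0.8.

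| Subjects per dose | Fisher + Kruskal-Wallis | Fisher + ANOVA | Chi-square + Kruskal-Wallis | Chi-square + ANOVA |
|---|---|---|---|---|
| 3/3/3 | 13.0 / 11.9 / 10.4 | 20.7 / 20.4 / 16.0 | 20.9 / 19.3 / 17.4 | 28.6 / 25.7 / 20.9 |
| 3/6/3 | 19.0 / 16.4 / 14.0 | 22.1 / 18.9 / 16.6 | 26.8 / 25.1 / 22.4 | 31.2 / 28.6 / 22.2 |
| 6/6/6 | 18.3 / 18.2 / 13.7 | 20.1 / 18.9 / 14.3 | 27.8 / 23.5 / 19.0 | 29.0 / 25.9 / 20.2 |
| 3/3 (two doses only) | 27.3 / 25.8 / 20.5 | 15.0 / 13.2 / 11.5 | 30.3 / 26.7 / 21.8 | 20.0 / 17.3 / 14.0 |

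The overall range is 10.4% to 31.2%. With three doses the low end is Fisher with Kruskal-Wallis and the high end is chi-square with ANOVA. With two doses of three, Kruskal-Wallis is the liberal choice. Complete separation gives H = 12/(6×7) × (6²/3 + 15²/3) − 3×7 = 3.86 and P = 0.0495, yet it occurs by chance in 2/20 = 10% of samples.

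**How much is test choice rather than number of tests.** Take the responder test at 3/3/3 with a 50% rate. The 5% critical value of chi-square on 2 df is 5.99. The response counts that exceed it, with their weights out of 2^9 = 512, are:

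- (3,0,0) and (3,3,0) in any order, chi-square 9.0: 3 + 3 = 6
- (3,1,0) and (3,2,0) in any order, chi-square 6.3: 6×3 + 6×3 = 36

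The next largest value, 5.14 for (2,0,0), does not reject. True size = 42/512 = 8.2%.

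In the same setting Fisher and Kruskal-Wallis each reject in about 1% of null trials or less, so this one test supplies most of the 10-13% in the first cell. A separate run at correlation 0.5 left it out and kept the other four efficacy tests (Fisher for mRS). It gave 4.3% at 3/3/3 with Kruskal-Wallis, but 13.5% at 3/3/3 with ANOVA and 11-15% at 3/3/6 or 6/6/6.

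**Would an alpha adjustment work?** Bonferroni over seven tests gives 0.05/7 = 0.0071. The smallest attainable P at 3/3/3 is:

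- Fisher: 3/84 = 0.036
- Kruskal-Wallis: H = 7.2, exp(−3.6) = 0.027
- Chi-square: 9.0, exp(−4.5) = 0.011

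None of these three tests could ever pass.

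**Not counted.** The adjusted mRS model, repeated time points, the per-protocol reanalysis and the synopsis's inter-group tests. Each is a further opportunity for P<0.05.

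**The case against.** The strongest reply is that this is a phase I study, titled exploratory, aiming at safety, the MTD and preliminary efficacy. Its primary outcome is DLT, and multiplicity handling commonly sits in a statistical analysis plan. Much of that stands. Several stronger readings that a reader might infer are not supported:

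- *That a promised 5% error rate is broken.* The protocol promises none; 0.05 is a per-test threshold, and a phase I trial without a confirmatory efficacy claim does not need familywise control.
- *That false results would steer dosing.* Escalation, MTD and stopping follow DLT counts (sections 1(2), 2(7), 11(6)). The protocol does aim to determine an appropriate dose, but no passage ties a P-value to that choice.
- *That the outcomes are unranked.* Section 11(3) names mRS 0-2 primary and the other efficacy outcomes secondary. Only a testing order is absent.
- *That nothing is called exploratory.* The study is; the section 11 tests are not.
- *That multiplicity explains the whole excess.* In the 3/3/3 Kruskal-Wallis case it is mainly the chi-square responder test.

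It is also fair to say that AE and SAE tests are not ordinarily alpha-controlled, since adjustment could hide signals.

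What the reply does not remove is the stated rule. Section 11(5) says which results will be called significant. That is text in the protocol, not a detail left for later.

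**Conclusion.** The point holds as a minor one. The protocol attaches a significance label to any of seven between-dose tests in small, sequentially filled cohorts and does not say that the P-values are nominal. With no dose effect, the chance that at least one earns the label is roughly 10-30%. That range rests on assumed event rates, correlations of 0 to 0.8, the group sizes shown and one-way ANOVA in place of repeated measures. A narrower figure would need inputs the protocol does not give. The direction is firm: every simulated setting of the full family is at least twice 5%. The consequence is confined to how efficacy and safety differences are described. Escalation and the DLT endpoint are untouched.

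**What to change.** In sections 11(3) and 11(5), and in the synopsis row on statistical methods:

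1. State that the DLT-based rule is the only decision-making analysis.
2. State that all between-dose comparisons of efficacy, AEs and SAEs are exploratory, with nominal P-values not adjusted for multiplicity.
3. Remove the statistical-significance rule for these comparisons.
4. Report per-dose estimates with 95% confidence intervals, exact for proportions. These show the uncertainty directly: with 3 of 3 responders the exact lower limit is 0.025^(1/3) = 29%, and with 0 of 3 the upper limit is 1 − 0.29 = 71%.

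The cost is wording and a small change to the tables, with no extra subjects, data or procedures. The downside is that an isolated P<0.05 can no longer be reported as a significant dose effect.
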